- Their condition of a concurrent disease (excluding the index stroke) deteriorates, requiring alternative treatment that conflicts with the study protocol; if the subject's stroke condition deteriorates after receiving hUC-MSC-sEV-001 (e.g., progression of neurological deficit), they shall withdraw from the study and be classified as an invalid case (not a lost-to-follow-up case);
- They have poor compliance (e.g., missed ≥ 2 scheduled visits, refusal to undergo required assessments) or express unwillingness to continue the study;
- They are lost to contact for ≥ 2 weeks despite repeated attempts (e.g., telephone, text message, home visit).

For lost-to-follow-up subjects, the investigator shall make every effort to complete the final safety assessment (e.g., vital signs, adverse event recording) and document the reason for withdrawal in the CRF.

(5) Provisions for Excluded Cases

A case is excluded from the efficacy analysis set if:

- The subject is misdiagnosed (e.g., final diagnosis is transient ischemic attack rather than ischemic stroke);
- The subject meets the inclusion criteria but is not administered any dose of hUC-MSC-sEV-001, or fails to receive scheduled doses due to production failure of the study drug;
- The subject participates in another interventional clinical trial during the study period;
- The subject receives prohibited combined medications (e.g., antineoplastic drugs, neurotrophic factors) or non-protocol-specified treatments that affect efficacy assessment;
- The subject has no evaluable efficacy data (e.g., no post-baseline NIHSS or mRS assessment);
- The subject has severe protocol violations (e.g., administration of the wrong dose, missed ≥ 3 doses).

Excluded cases shall be documented in the "Protocol Deviation Log", and their CRFs shall be retained for audit. Subjects who receive at least one dose of the study drug and have safety data shall be included in the safety analysis set.

(6) Criteria for Terminating or Withdrawing from the Study

i. Study Termination

Study termination refers to the early cessation of the entire study before completion of the planned protocol. The decision to terminate the study shall be made by the sponsor, principal investigator, or Ethics Committee, and shall be documented in the "Study Termination Report". Reasons for termination include:

- Emergence of SAEs that suggest a causal relationship with the study drug and pose a serious risk to subjects;

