- Confirmation of the MTD or identification of an unsafe dose level;
- Major flaws in the study design that affect data validity;
- Regulatory requirements (e.g., request by the National Medical Products Administration [NMPA]).

. Subject Withdrawal

Subjects may withdraw from the study at any time for the following reasons:

(1) Investigator-determined withdrawal:

① The subject develops a medical condition that makes continued participation unsafe (e.g., severe allergic reaction, intracranial hemorrhage);② The subject uses medications that interact with the study drug (e.g., immunosuppressants) or affect efficacy assessment (e.g., edaravone);③ The subject experiences a SAE that requires termination of study participation;④ The subject has poor compliance that compromises the reliability of safety or efficacy data.

(2) Subject-initiated withdrawal:

① The subject voluntarily requests to withdraw (no reason required);② The subject is lost to follow-up (no contact for ≥ 2 weeks).

For withdrawn subjects, the investigator shall conduct a final safety assessment (if possible) and document the reason for withdrawal in the CRF. Subjects who withdraw due to AEs/SAEs shall receive appropriate medical treatment, and follow-up shall continue until the AE/SAE resolves or stabilizes.

(7) Criteria for Terminating the Study

The study will be terminated immediately if any of the following occurs:

≥ 2 subjects experience DLT at the same dose level (indicating that the dose exceeds the MTD);

- Production of hUC-MSC-sEV-001 fails to meet quality standards for 3 consecutive batches, resulting in inability to administer scheduled doses;

- The study drug is found to have no clinical benefit (e.g., no improvement in neurological function in all enrolled subjects) or is associated with unexpected severe toxicity;
- A major protocol deviation is identified (e.g., incorrect randomization, unapproved dose modification) that invalidates the study results;
- The sponsor terminates the study due to funding, strategic adjustments, or other reasons;
- The Ethics Committee or NMPA issues an order to terminate the study.

3. Intervention Measures

(1) Trial Drug

- **Generic Name:** Human Umbilical Cord Mesenchymal Stromal Cell-Derived Small Extracellular Vesicle (hUC-MSC-sEV-001) Nasal Drops
- **Source:** Isolated and purified from the supernatant of hUC-MSCs cultured under GMP conditions

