1. **Dose Adjustment:** No dose reduction is allowed during the study. If a subject experiences a Grade ≥ 3 AE, study drug administration is suspended until the AE resolves to Grade ≤ 1 ; if the AE is judged to be related to the study drug, the subject withdraws from the study.

2. **Prohibited and Restricted Medications:**

- Prohibited medications: Antineoplastic drugs, immunosuppressants (e.g., cyclosporine, tacrolimus), neurotrophic factors (e.g., nerve growth factor);
- Restricted medications: Antibiotics and antiviral drugs (used only for confirmed infections, with duration documented); non-steroidal anti-inflammatory drugs (NSAIDs) (avoided if possible to reduce bleeding risk).

3. **Concurrent Diseases Management:** If a subject develops a concurrent disease (e.g., pneumonia, myocardial ischemia) during the study, the treating physician provides standard treatment, and the details are documented in the "Concurrent Disease Record Form" in the CRF.
4. **Subject Education:** Subjects are instructed to report any new symptoms (e.g., headache, nasal congestion, rash) to the investigator immediately, and to avoid self-medication with prohibited drugs.

4. Observation Items

(1) Demographic and Clinical Data

1. **Demographic Characteristics:** Gender, age, date of birth, ethnicity, dominant hand, occupation, height, weight, body mass index (BMI);
2. **Clinical History:** Chief complaint, onset time of stroke, detailed history of present illness, primary diagnosis (including infarct location), secondary diagnoses, past medical history (hypertension, diabetes, hyperlipidemia, coronary heart disease), surgical history, allergy history, family history, smoking history (pack-years), drinking history (alcohol consumption per week);
3. **Medication History:** Current medications (including over-the-counter drugs, herbal supplements) at screening, with dosage, frequency, and duration documented.

All data are recorded in the "Baseline Demographic and Clinical Data Form" in the CRF.

(2) Safety Observation Indicators

1. **Vital Signs:** Measured before each dose administration and at each follow-up visit:
 - Pulse (beats per minute), blood pressure (mmHg, measured in the sitting position after 5 minutes of rest), respiratory rate (breaths per minute), body temperature (°C, axillary or oral);
 - Abnormal vital signs (e.g., hypertension: systolic blood pressure ≥ 160 mmHg) are documented and followed up.
2. **Laboratory Tests:**

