1. Neurological Function Scales:

- **NIHSS:** Assesses the severity of neurological deficits (range: 0-42; higher scores indicate more severe deficits). Administered at baseline, Day 7, Day 14, and Day 90.
- **mRS:** Assesses functional independence (range: 0-6; scores 0-2 indicate good functional outcome). Administered at baseline, Day 7, Day 14, and Day 90.
- **Modified Barthel Index (MBI):** Assesses activities of daily living (range: 0-100; higher scores indicate better independence). Administered at baseline, Day 14, and Day 90.
- **EQ-5D-5L:** Assesses health-related quality of life (including mobility, self-care, usual activities, pain/discomfort, anxiety/depression; scored as a utility value ranging from -0.291 to 1.0). Administered at baseline, Day 14, and Day 90.

2. Cerebral Perfusion Parameters (CTP):

- Measured at baseline, Day 14, and Day 90: cerebral blood volume (CBV), cerebral blood flow (CBF), mean transit time (MTT), time to peak (TTP) in the infarct core and penumbra.
- Changes in perfusion parameters from baseline are used to evaluate the improvement of cerebral blood flow.

3. Infarct Volume Measurement:

- Infarct volume is measured on DWI using the ABC/2 method (A: maximum length, B: maximum width perpendicular to A, C: number of slices × slice thickness).
- Changes in infarct volume from baseline to Day 14 are used to evaluate infarct progression or regression.

5. Outcome Evaluation Indicators

(1) Primary Safety Endpoints

- **Dose-Limiting Toxicity (DLT):** Assessed within 14 days of the first dose, defined as any of the following:
 1. Grade 3-4 AE related to the study drug (CTCAE V5.0), such as severe nasal bleeding, anaphylactic reaction, or hepatic injury;
 2. Increase in NIHSS score ≥ 4 points from baseline (indicating significant neurological deterioration);
 3. Symptomatic intracranial hemorrhage (confirmed by CT/MRI and associated with neurological deterioration).

(2) Secondary Safety Endpoints

1. **SAE Incidence:** Proportion of subjects with drug-related SAEs within 90 days of the first dose;
2. **All-Cause Mortality:** Proportion of subjects who die from any cause within 90 days of the first dose;
3. **Laboratory Abnormality Rate:** Proportion of subjects with Grade ≥ 3 laboratory abnormalities (e.g., thrombocytopenia, elevated liver enzymes) within 90 days.

(3) Efficacy Endpoints

1. **Functional Outcome:** Proportion of subjects with mRS score 0-2 at Day 90;

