- **Grade 1-2 AEs:** Monitor closely; provide symptomatic treatment if needed (e.g., antihistamines for mild rash). Continue study drug administration if the AE is judged to be unrelated or unlikely related to the study drug.
- **Grade 3-4 AEs:** Suspend study drug administration immediately; provide urgent medical treatment (e.g., corticosteroids for severe allergic reactions). The investigator assesses the causal relationship between the AE and the study drug. If the AE is related or probably related, the subject withdraws from the study, and follow-up continues until the AE resolves or stabilizes.
- **SAEs:** Implement the following emergency procedures:
 1. Provide immediate medical treatment to stabilize the subject's condition;
 2. Notify the principal investigator, sponsor, and Ethics Committee within 24 hours of awareness;
 3. Complete the "Serious Adverse Event Report Form" and submit it to the Ethics Committee and sponsor;
 4. Conduct follow-up assessments until the SAE resolves or stabilizes, and submit follow-up reports every 7 days until resolution.

(4) Assessment of Causal Relationship Between Adverse Events and Study Drug

The causal relationship is assessed by the investigator based on the following five factors:

1. **Temporal Relationship:** Whether the AE occurred after administration of the study drug (onset time within the drug exposure period);
2. **Known Pharmacological Effects:** Whether the AE is consistent with the known safety profile of MSC-sEVs (e.g., nasal irritation is a potential local effect);
3. **Decchallenge Response:** Whether the AE resolved or improved after discontinuing the study drug;
4. **Rechallenge Response:** Whether the AE recurred after re-administering the study drug (not applicable in this study due to safety concerns);

5. **Alternative Etiologies:** Whether the AE can be explained by the subject's underlying disease, concurrent medications, or other factors.

The causal relationship is classified into five categories:

- **Definite:** All five factors support a causal relationship;
- **Probable:** Four factors support a causal relationship, and no alternative etiology is identified;
- **Possible:** Three factors support a causal relationship, and alternative etiologies are possible;
- **Unlikely:** Two or fewer factors support a causal relationship, and alternative etiologies are likely;
- **Unrelated:** No factors support a causal relationship, and alternative etiologies are confirmed.

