- **Source Documents:** Medical records, laboratory reports, imaging films, and informed consent forms are stored in the hospital's medical record department or study office for 30 years after study completion.
- **Electronic Data:** The EDC database and backup files are stored on a secure server with restricted access. The data are retained for 30 years after study completion.
- **Statistical Analysis Data:** The locked database and statistical analysis code are stored in a secure location and retained for 30 years after study completion.

11. Statistical Analysis

(1) Statistical Analysis Sets

- **Full Analysis Set (FAS):** Includes all randomized subjects who receive at least one dose of the study drug. Missing efficacy data are imputed using the last observation carried forward (LOCF) method.
- **Per Protocol Set (PPS):** Includes subjects in the FAS who comply with the study protocol (e.g., complete all visits, receive all 4 doses of study drug, no major protocol violations). This set is used for sensitivity analysis of efficacy outcomes.
- **Safety Analysis Set (SAS):** Includes all subjects who receive at least one dose of the study drug. This set is used for safety analyses (adverse events, laboratory abnormalities).

(2) Descriptive Statistics

- **Continuous Variables:** Presented as mean \pm standard deviation (SD) for normally distributed data, or

median (P25, P75) for non-normally distributed data. Examples include age, NIHSS score, and infarct volume.

- **Categorical Variables:** Presented as frequency (percentage). Examples include gender, hypertension status, and mRS score categories (0-2 vs. 3-6).

(3) Inferential Statistics

- **Primary Efficacy Endpoint:** The proportion of subjects with mRS score 0-2 at Day 90 is compared between dose groups using the chi-square test or Fisher's exact test. A generalized linear model is used to adjust for potential confounders (e.g., age, baseline NIHSS score).
- **Secondary Efficacy Endpoints:**
 - Mean changes in NIHSS, MBI, and EQ-5D-5L scores from baseline are compared using repeated measures analysis of variance (ANOVA) or Kruskal-Wallis rank sum test.
 - The proportion of subjects with NIHSS score reduction ≥ 4 points at Day 14 is compared using the chi-square test.
- **Safety Endpoints:**
 - The incidence of AEs and SAEs is compared between dose groups using the chi-square test or Fisher's exact test.

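### The per-protocol set requires every visit to be completed, so it leaves out deaths and subjects the protocol itself withdraws, and is a weak robustness check for efficacy

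*Protocol*

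**What the plan says.** Section 11(1) defines three sets. The full analysis set (FAS) holds treated subjects, with missing efficacy data filled by last observation carried forward. The safety set holds everyone with at least one dose. The PPS is a subset of the FAS: "Includes subjects in the FAS who comply with the study protocol (e.g., complete all visits, receive all 4 doses of study drug", with no major violations as the remaining example. Its purpose is stated: "This set is used for sensitivity analysis of efficacy outcomes".

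The visits are Day 0, Day 7, Day 14 and Day 90 (section 6). For NIHSS and mRS, section 4(3) says: "Administered at baseline, Day 7, Day 14, and Day 90".

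Other sections end participation because of what happens to the subject:
- Section 2(4), stroke deterioration after dosing: "they shall withdraw from the study and be classified as an invalid case".
- Section 3(4), Grade 3 or higher adverse event: "if the AE is judged to be related to the study drug, the subject withdraws from the study".
- Section 8(3), Grade 3-4 adverse event: "If the AE is related or probably related, the subject withdraws from the study".
- Section 2(6), investigator-determined withdrawal: "The subject experiences a SAE that requires termination of study participation".

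For withdrawn subjects, section 2(6) says "the investigator shall conduct a final safety assessment (if possible) and document the reason for withdrawal in the CRF". Follow-up of the adverse event continues, but no Day 90 efficacy assessment is required.

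**The concern.** A per-protocol set is meant to separate subjects treated and assessed as planned from those who were not. Here a subject can follow every instruction and still be excluded, because he or she died or because the protocol required withdrawal. Those events are outcomes of the disease or of treatment, not failures of compliance.

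The link to efficacy is direct. The mRS runs to 6, its category for death, and section 11(2) groups 3-6 as the poor category, so a death before Day 90 is a known failure on the mRS 0-2 endpoint. Deterioration is also what the NIHSS change endpoint in section 5(3) measures. An analysis intended to test the FAS result would therefore drop some of the worst results from both endpoints. With 3 or 6 subjects per dose level, one such removal visibly moves the percentage.

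**Working it through.** The protocol states no figure for this point, so there is none to reproduce. The check has a logical part and an illustrative part.

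**1. Who can meet the rule**

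| Event before Day 90 | Source | Can complete all visits? | Known mRS 3-6? |
|---|---|---|---|
| Death | 5(2), an endpoint | No | Yes (mRS 6) |
| Stroke deterioration | 2(4), mandatory withdrawal | No Day 90 efficacy visit required | Likely, not certain |
| Related Grade 3 or higher AE | 3(4), 8(3), mandatory withdrawal | No Day 90 efficacy visit required | Not known |
| Stable at mRS 3-5, attends all visits | none | Yes | Yes, and stays in |

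Section 11(1) exempts none of the first three rows.

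**2. Effect on the mRS 0-2 rate**

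Let n be the number treated, g the number at mRS 0-2 and r the number removed. If everyone removed is at mRS 3-6, the rate is g/n in all treated and g/(n − r) in the PPS. The counts below are assumed.

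| n | g | r | All treated | PPS | mRS 3-6 still in PPS |
|---|---|---|---|---|---|
| 3 | 1 | 1 | 1/3 = 33.3% | 1/2 = 50.0% | 1 |
| 6 | 2 | 1 | 2/6 = 33.3% | 2/5 = 40.0% | 3 |
| 6 | 2 | 2 | 2/6 = 33.3% | 2/4 = 50.0% | 2 |
| 18 | 6 | 2 | 6/18 = 33.3% | 6/16 = 37.5% | 10 |
| 18 | 6 | 4 | 6/18 = 33.3% | 6/14 = 42.9% | 8 |
| 18 | 6 | 6 | 6/18 = 33.3% | 6/12 = 50.0% | 6 |

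The last column shows that poor outcomes remain in the PPS in every case.

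**3. When the direction reverses**

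If the one subject removed was withdrawn for toxicity but would have reached mRS 0-2, then with n = 6 and g = 2 the PPS gives 1/5 = 20.0%, below 33.3%. Upward bias is certain for deaths, likely for deterioration and uncertain for toxicity withdrawals.

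**4. Comparison between doses**

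Take two levels of three, each with one success. One death at the higher level only turns 1/3 against 1/3 into 1/3 against 1/2, an apparent advantage for the dose with the death. One death at each level gives 1/2 against 1/2: both rates rise, but no difference appears.

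**5. How often this would arise**

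The protocol gives no rate for death or mandated withdrawal. For an assumed combined probability d per subject, the chance of at least one removal is 1 − (1 − d)^n:

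| d | n = 6 | n = 18 |
|---|---|---|
| 5% | 26.5% | 60.3% |
| 10% | 46.9% | 85.0% |
| 20% | 73.8% | 98.2% |
| 30% | 88.2% | 99.8% |

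**The case against.** The strongest reply is that little depends on this set. The primary endpoint is dose-limiting toxicity, and no escalation, MTD or stopping rule uses the PPS. Deaths and toxicity are reported in the safety set, and the FAS is kept for efficacy. A study that ends at two DLTs on one dose level also limits early removals. All of this stands, and it keeps the point modest. It does not make the PPS informative for its one stated use, and the DLT rule does not limit deaths after the 14-day window. The FAS is not a clean fallback either: it carries the last observation forward, and no stated rule scores death as mRS 6.

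A second reply is that the criteria are only examples and that final set rules usually belong in the statistical analysis plan. That plan may refine them. But these are the only criteria the protocol gives, and completion of every visit is named outright.

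A third reply is that per-protocol sets are commonly selective and are secondary for that reason. That is fair, but here the selection includes withdrawals that the protocol itself orders.

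Two stronger readings are tempting and should not be drawn. A reader might infer that the PPS contains only subjects who did well. It does not: membership sets no mRS threshold, so a stable subject at mRS 3-5 who attends every visit is included and counts as a failure. A reader might also infer that the PPS would make an inert product appear effective. There is no control arm, and section 11(3) compares dose groups, so similar removals across doses raise the absolute rates without creating a dose difference.

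**Conclusion.** The point holds in a limited form. As written, PPS membership depends on surviving to Day 90 and on not being withdrawn for worsening or related toxicity. Absolute mRS 0-2 rates are inflated whenever the subjects removed are deaths or other poor outcomes, and dose comparisons are distorted if harm differs by dose. One removal can move a dose-level rate from 33% to 50% with three subjects, or from 33% to 40% with six. These figures rest on assumed counts and on the removed subject being at mRS 3-6. The set is therefore a weak robustness check on efficacy. Safety conclusions and dose decisions are not affected. The definition should be changed before any outcome data are seen.

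**What to change.** Amend the PPS definition in section 11(1):
- Base membership on eligibility, dosing as assigned and absence of major deviations, each judged up to death or protocol-mandated withdrawal.
- Replace the all-visits condition with having a Day 90 mRS or having died, and state that withdrawal required by the protocol is not non-compliance and does not remove a subject.
- Score death as mRS 6.
- For mandated withdrawals, use the Day 90 mRS where available. Where it is unknown, show the mRS 0-2 result twice, with these subjects counted as non-success and as success. Counting every toxicity withdrawal as a failure would be a debatable fixed rule, since some may recover well.

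Example with assumed counts: of six subjects, two are at mRS 0-2, two at mRS 3-5, one has died and one was withdrawn with Day 90 mRS unknown. The current rule gives 2/4 = 50.0%. The revised set gives 2/6 = 33.3% with the unknown as non-success and 3/6 = 50.0% with it as success.

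The cost is a few lines of text, with no added subjects and no change to any clinical rule. The PPS result may look slightly less favourable and will lie closer to the FAS. Because section 2(6) asks only for a final safety assessment after withdrawal, the two-way display may often be needed.

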Study design		Using a traditional "3+3" dose-escalation design, subjects will be sequentially assigned to one of three dose groups (2.8×10^{10} units, 1.4×10^{11} units, and 7.0×10^{11} units per dose, once daily, with continuous intranasal instillation for 4 days). Each dose group will include 3 subjects, who will be enrolled one by one. The exploration of the next dose can only proceed if no dose-limiting toxicity (DLT) is observed in the 3 subjects. If 1 out of the 3 subjects experiences DLT, an additional 3 subjects will be enrolled in the same dose group; the exploration of the next dose can only move forward if no DLT is observed in these newly added 3 subjects. A minimum of 6 and a maximum of 18 subjects will be recruited during the dose exploration phase. Patients will receive other standard medical treatments in accordance with the recommendations in the 2022 Chinese Guidelines for Secondary Prevention of Ischemic Stroke and Transient Ischemic Attack , including antiplatelet drugs or anticoagulants, antihypertensive drugs, lipid-lowering drugs, and glucose-lowering drugs.
Outcome Measures	Primary Outcome Measure	Dose-Limiting Toxicity (DLT) Related to hUC-MSC-sEV-001 Includes: (1) Grade 3-4 severe adverse events occurring on day 14 (+-2), graded according to Common Terminology Criteria for Adverse Events (CTCAE) V5.0; (2) NIHSS score increase of ≥ 4 from baseline on day 14 (+-2); NIHSS score assessed by a professional rehabilitation physician;(3) Symptomatic intracranial hemorrhage occurring on day 14 (+-2); detected via CT scan and patient symptom presentation.
	Secondary Outcome Measures:	Serious adverse events related to the investigational drug within 90 (+-7) days. Distribution of Modified Rankin Scale (mRS) Scores within 90 (+-7) days. Barthel Index within 90 (± 7) days. Five-level, five-dimensional EuroQol (EQ-5D-5L) . Proportion of Modified Rankin Scale (mRS) Scores of 0-2 within 90 (+-7) days. All-cause mortality at 90 (+-7) days. Changes in infarct volume at 14 (+-2) days compared to baseline. Change from Baseline in National Institutes of Health Stroke Scale (NIHSS) Score.
Follow-up duration		Baseline (0~1 day), 7 (± 1) days, 14 (± 2) days, 90 (± 7) days
Sample size		6-18 subjects need to be included.

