Statistical Analysis Methods	
The primary objective of this study is to evaluate the safety and preliminary efficacy of hUC-MSC-sEV-001 nasal drops (small extracellular vesicles derived from human umbilical cord mesenchymal stem cells) in the treatment of acute ischemic stroke. Baseline information will be described based on the distribution type of variables: continuous variables will be presented as mean \pm standard deviation, as well as P50, P25, and P75 percentiles; categorical variables will be described using frequency (percentage). For inter-group differences: analysis of variance (ANOVA) or Kruskal-Wallis rank sum test will be used for continuous variables; chi-square test or Fisher's exact test will be used for categorical variables. A generalized linear model will be applied to analyze the difference in the proportion of patients with a modified Rankin Scale (mRS) score of 0-2 at 90 days (± 7 days) between the two groups.

------------------------------	---

Research Background

The prevention and treatment of brain diseases is a major challenge for "Healthy China". While stem cells have made significant progress in the treatment of brain diseases, they have limitations such as immune rejection and poor histocompatibility. Stem cell derivatives, such as exosomes or small extracellular vesicles (sEVs), exhibit similar therapeutic effects to stem cells. Moreover, their low immunogenicity and ability to easily cross the blood-brain barrier give them greater advantages in the treatment of brain diseases.

This research focuses on the therapeutic effects and mechanisms of four types of stem cell-derived sEVs in ischemic stroke and Alzheimer's disease (AD), with the goal of advancing their clinical research and application. The study addresses key scientific issues, including the mechanism by which stem cell-derived sEVs regulate neuronal target cells and immune microenvironment cells *in vivo* to achieve stem cell-like functions. It will also provide a safe and efficient mesenchymal stem cell-derived sEV (MSC-sEV) therapeutic protocol for solving global challenges such as ischemic stroke and AD.

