Single-center, prospective, dose-escalation clinical trial.

(2) Trial Administration Strategy

A traditional "3+3" dose-escalation design will be adopted. Subjects will be sequentially assigned to one of three dose groups (2×10^{10} units, 1×10^{11} units, 5×10^{11} units per administration, once daily for 4 consecutive days via intranasal instillation). Each dose group initially enrolls 3 subjects, with sequential enrollment (i.e., the next subject is enrolled only after the previous subject completes the 14-day DLT observation period).

- If no DLT is observed in 3 subjects of a dose group, the study proceeds to the next higher dose level.

- If 1 out of 3 subjects experiences DLT, an additional 3 subjects are enrolled in the same dose group. If no DLT is observed in the additional 3 subjects, the study proceeds to the next higher dose level; if ≥ 1 additional subject experiences DLT, the current dose level is defined as the maximum tolerated dose (MTD), and dose escalation is terminated.
- A total of 6 to 18 subjects will be recruited during the dose-escalation phase.

(3) Study Suspension or Early Termination

The study will be suspended or terminated early if any of the following occurs:

- Violation of the *Good Clinical Practice (GCP)* or the *Administrative Measures for Stem Cell Clinical Research (Trial)*;
- Emergence of new safety or efficacy data on MSC-sEVs indicating that the trial poses a serious risk to patient safety or is clearly ineffective;
- Failure to enroll subjects as scheduled for 3 consecutive months;
- Major protocol deviations that affect the validity of study data;
- Request for termination by the sponsor or regulatory authorities.

2. Subject Selection Criteria

(1) Inclusion Criteria

- Confirmed diagnosis of acute ischemic stroke (in accordance with the *Chinese Guidelines for the Diagnosis and Treatment of Acute Ischemic Stroke (2023)*);
- Aged 18-70 years, regardless of gender;
- Anterior circulation occlusion (internal carotid artery, middle cerebral artery M1/M2 segment) confirmed by CTA or MRA;
- mRS score of 0-1 before the current stroke episode (indicating no or minimal disability prior to the index event);
- ASPECTS ≥ 6 on non-contrast computed tomography (NCCT) or diffusion-weighted imaging (DWI) after stroke onset (indicating a small to moderate infarct volume);
- NIHSS score ≥ 6 at screening (indicating moderate to severe neurological deficit);

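### The covariate-adjusted generalized linear model for mRS 0-2 at Day 90 usually has no finite estimate at the sample sizes this 3+3 design most often yields

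*Protocol*

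**What the plan says.** Section 11(3) of the Protocol labels mRS 0-2 at Day 90 the primary efficacy endpoint. It first says that the proportion "is compared between dose groups using the chi-square test or Fisher's exact test". It then adds: "A generalized linear model is used to adjust for potential confounders", giving age and baseline NIHSS score as examples. Section 11(5) sets two-sided tests at 0.05.

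The synopsis (Statistical Analysis Methods) gives chi-square or Fisher's test for categorical variables in general. For this endpoint in particular it names only the model: "A generalized linear model will be applied to analyze the difference in the proportion of patients with a modified Rankin Scale (mRS) score of 0-2", and places the comparison "between the two groups".

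The design has three groups, not two. Section 1(2) says: "Subjects will be sequentially assigned to one of three dose groups", and "Each dose group initially enrolls 3 subjects, with sequential enrollment". A group grows to six only after one DLT among its first three subjects. The stated total is 6 to 18. The link function, the coding of dose and the handling of non-convergence are not stated.

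**The concern.** Comparing three dose groups with two covariates takes five parameters: an intercept, two dose contrasts, age and NIHSS. If all three doses are reached without expansion, there are nine binary outcomes to fit them to. If a dose group has no responders or only responders, or if the covariates happen to split responders from non-responders, the likelihood has no finite maximum. Software then prints very large coefficients with meaningless standard errors, and these would be read against p<0.05. At stake is the only covariate-adjusted efficacy estimate in the plan. There is also a risk that a replacement model is chosen after the data have been seen.

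**Working it through.** **Inputs from the Protocol.** Three dose groups; 3 subjects each, 6 after expansion; total 6-18; binary endpoint; example covariates age (18-70) and NIHSS (6 or more); two-sided 0.05. The Protocol gives no figure for whether the model can be estimated, so there is none to reproduce.

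**Assumptions, not in the Protocol.** mRS 0-2 rate 30-50%, equal across doses; logit link; age and NIHSS drawn from plausible distributions, with and without an association with outcome.

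**Step 1: how large the trial is likely to be.** Take DLT rates of 5/10/20% as an example. The chance of the 3/3/3 layout is 0.95³ × 0.90³ × (1 − 3 × 0.20 × 0.80²) = 0.857 × 0.729 × 0.616 = 0.385. The chance of 3/3/6 is 0.857 × 0.729 × 0.384 = 0.240. Over all paths the total is 9 in 44% of trials, 12 in 39%, 15 in 10% and 18 in 1%. Across nine sets of assumed DLT rates, from 1/2/5% to 20/35/50%, the total is 12 or fewer in at least 86% of trials, and 18 in at most 1.5%.

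**Step 2: empty or full dose groups, before any covariate.** With rate p and n subjects, one group is all-equal with probability q = pⁿ + (1−p)ⁿ. The chance that at least one of three equal groups is all-equal is 1 − (1−q)³.
- n = 3, p = 0.3: q = 0.027 + 0.343 = 0.370; 1 − 0.630³ = 75.0%
- n = 3, p = 0.4: q = 0.280; 1 − 0.720³ = 62.7%
- n = 3, p = 0.5: q = 0.250; 1 − 0.750³ = 57.8%
- n = 6, p = 0.3: q = 0.1184; 1 − 0.8816³ = 31.5%
- n = 6, p = 0.5: q = 0.03125; 1 − 0.96875³ = 9.1%

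Each such data set already makes a dose-group odds ratio infinite or undefined.

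**Step 3: with age and NIHSS added.** Data sets were simulated (1,000-1,500 per setting) and complete or quasi-complete separation was detected by linear programming. The ranges cover rates of 30-50% and the covariate assumptions tried.

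| Layout | Dose coding | No finite estimate |
|---|---|---|
| 3/3/3 | three-level factor | 71-85% |
| 3/3/6 | three-level factor | 48-69% |
| 6/6/6 | three-level factor | 9-34% |
| 3/3/3 | one linear term | 36-56% |
| 6/6/6 | one linear term | 1-6% |

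**Step 4: hand check.** Cover's formula gives the chance that n randomly labelled points (rate 50%) are completely separable with d parameters: the sum of C(n−1, k) for k = 0 to d−1, divided by 2ⁿ⁻¹. For n = 9, d = 4 it is 93/256 = 36.3%, against 35.9% simulated for linear dose. For n = 9, d = 5 it is 163/256 = 63.7%. This is a floor for the factor model, because all-equal groups add quasi-separation.

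**Step 5: precision when the model does fit.** With 3/3/3, dose as a factor and prognostic covariates, the median standard error of the high-versus-low log odds ratio is 2.53 to 2.92 over rates of 20-60%. A 95% interval then extends by a factor of exp(1.96 × 2.53) ≈ 142 to exp(1.96 × 2.92) ≈ 306 in each direction.

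**Step 6: the first-named test.** Fisher's exact test on the three-group 3/3/3 table can always be computed. Its smallest p arises when three responders all fall in one group: 3/C(9,3) = 3/84 = 0.036. Under no effect, the chance of p<0.05 is about 1.0-1.2% at rates of 30-50%. At 50% it is 6/512 = 1.2%.

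**The case against.** The strongest reply is that section 11(3) names chi-square or Fisher's exact test first and adds the model only as an adjustment. Section 11(2) already plans frequencies for mRS 0-2 versus 3-6. Escalation and the MTD rest on DLT, and no section uses the mRS model to choose a dose. All of this stands. A reader might infer that the main efficacy analysis as a whole gives no valid result, or that dose choice loses its basis. The Protocol supports neither reading. Nor is significance out of reach for the planned test: a 3-versus-3 pairwise Fisher test cannot go below 0.10, but the Protocol names no pairwise test, and the three-group minimum is 0.036.

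It can also be said that the five-parameter model is one reading. Age and NIHSS are given as examples, and the link and dose coding are unstated and may be settled in a statistical analysis plan that is not shown. The synopsis speaks of a difference in proportions, which need not mean a logit link. This stands in part. Linear dose lowers the failure rate, and at 18 subjects failure is the exception. But the use of the model, its example covariates and the significance level are fixed in the Protocol with no small-sample condition. Even linear dose fails in a third to a half of nine-subject data sets, and other links also have trouble when observed proportions are 0 or 1.

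The reference to two groups is a separate wording error and adds nothing to the separation argument.

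**Conclusion.** The point holds for the adjusted generalized linear model. At 9 subjects with dose as a factor, it has no finite estimate in roughly seven to eight and a half of every ten data sets; at 12 subjects (3/3/6), in about half to two thirds. These are the sizes the design most often yields under the assumed DLT rates. When the nine-subject factor model can be fitted, its estimate is too imprecise to use. The failure rates rest on a logit link, assumed mRS 0-2 rates of 30-50% and assumed covariate distributions; the 58-75% chance of an all-equal dose group at 3/3/3 needs only the response rate. The unadjusted exact test, the descriptive frequencies and the DLT-based escalation are unaffected. The matter should be corrected, but it does not threaten the trial's primary safety purpose.

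**What to change.** In section 11(3), replace the adjusted model with the number and proportion with mRS 0-2 per dose and pooled, each with an exact (Clopper-Pearson) 95% interval. These can always be computed and show the uncertainty openly: for 0/3 the interval runs from 0 to 1 − 0.025^(1/3) = 70.8%. If a comparison across doses is kept, prespecify one method: an exact trend test on ordered dose, or Firth-penalised logistic regression with a single dose score and at most baseline NIHSS as covariate.

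In the synopsis, change the two groups to the three dose groups and state the same mRS 0-2 analysis as section 11(3).

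The cost is Protocol wording, with no change to conduct, visits or sample size. The downside is an efficacy result that is less adjusted and openly descriptive.
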